Low Dose Ketamine Infusion for Analgesia in the Emergency Department to Reduce Side Effects

Study Protocol and Analysis Plan

NCT05518877

June 6, 2024

Study Title: Low Dose Ketamine Infusion for Analgesia in the ED to Reduce Side Effects: A Double Blind, Double Dummy Randomized Controlled Trial

Principle Investigator: PI: [name], DO
Sub-Investigator: Sub-I: [name]

Address: Summa Health Department of Emergency Medicine
[name]
[name]

1. Purpose of Study

Research has shown low dose ketamine (LDK) Intravenous push (IVP) (0.3mg/kg) to have equivalent pain reduction in moderate to severe acute pain in the Emergency Department (ED) when compared to standard of care of morphine IVP (0.1mg/kg). Ketamine has been shown to produce side effects in these studies, including dizziness, feeling of unreality and mood changes. There were no unexpected side effects or adverse events during this trial.¹ Another study compared IVP with a slower infusion of LDK and showed a decrease in side effects while maintaining similar analgesic efficacy. This trial found increased feelings of unreality for the IVP group (difference of 37.5%) as well as increased rates of sedation.²

In clinical practice, increasing the time/duration of the infusion has resulted in a decrease of reported side effects from patients while still maintaining analgesia. There have been no studies done to prove that there is a further reduction in side effects with a longer LDK infusion. We believe that increasing the infusion time to greater than 15 minutes will reduce the frequency and intensity of expected side effects of ketamine felt by recipients and allow for further use of ketamine as a non-opiate analgesic in the ED.

Overall aims of project:

1. Reduce overall incidence and severity of known side effects of low dose ketamine when given over 30 minutes versus 15 minutes.
2. Maintain adequate pain control, as determined by a Visual Analogue Score (VAS) of ≤ 5 cm (50mm) at 30 minutes after start of ketamine infusion.

Hypothesis: Slow infusion of LDK over 30 minutes will provide adequate pain control (as defined by VAS score of ≤ 5 cm (50mm)), and reduce incidence and severity (by at least 20% or 1 point on Side Effects Rating Scale for Dissociative Anesthetics [SERSDA] scale) of known side effects when compared to LDK given over 15 minutes in moderate to severe acute pain for patients presenting to the ED.

2. Background and Rationale

Ketamine is a phencyclidine derivative and functions as an antagonist of N-methyl-D-aspartate receptor (NMDA).³ Painful stimuli activate nociceptive neurons triggering the release of glutamate, which attach to NMDA receptors in the dorsal horn of the spinal cord.⁴ This triggers a cascade responsible for central sensitization and secondary hyperalgesia, also known as the “wind-up” phenomenon, making pain relief harder to achieve.^{3,4} NMDA receptors are also known to be involved in the development of opioid tolerance.⁴

Ketamine is FDA approved for anesthesia and procedural sedation but is known to have a long history of off label uses such as analgesia and treatment of depression. While the medication is not FDA approved for analgesia, it is not restricted for sole use as an anesthetic agent. It is generally accepted that off-label use of medications is acceptable at the sole discretion of the provider. Off-label use has spurred increase in research and has even led to FDA approval in the past, notably for intranasal esketamine for treatment-resistant depression in 2019.⁵ Many of the following articles show that ketamine can be used as a safe alternative for analgesia in the hospital setting, notably the Emergency Department.

Ketamine at low (sub-dissociative) doses of 0.1-0.3mg/kg, has been shown to improve pain scores as well as reduce perioperative opioid consumption with minimal side effects.⁴ At these sub-dissociative doses, it has produced hemodynamically stable anesthesia and analgesia with minimal measurable cardiovascular, respiratory, or gastrointestinal side effects.^{3,4}

In 2015, a prospective, randomized double blind trial compared low dose ketamine to morphine for analgesia and showed promising results. Patients received either 0.3mg/kg of ketamine or 0.1mg/kg of morphine for acute moderate to severe pain to study efficacy and safety profile. Similar rates of reduction in pain were found in both groups at all time points. The ketamine group had more reported side effects including dizziness, disorientation, mood changes and nausea at the five-minute mark (73% vs 51%) and at

the fifteen-minute mark (69% vs 31%) but they equalized with the morphine group at the thirty-minute mark (36% vs 33%).¹

Based on mentioned data, we hypothesized that increasing time for low dose ketamine infusion when used in the ED for analgesia will reduce side effects even further than what prior studies have shown. There are several research papers that support our hypothesis.

A prospective double-blind trial of 40 patients was conducted for acute musculoskeletal trauma pain with treatment groups receiving either intermittent morphine (0.1mg/kg every 4 hours IV) or continuous infusion of subcutaneous ketamine (0.1mg/kg/hr) after an initial bolus (0.25mg/kg). Pain was measured on a 10-point visual analog scale (VAS), along with 4-point sedation score and objective vital signs. There was statistically significant improvement in pain for the ketamine group starting at fifteen minutes which continued to the 24-hour mark. No significant changes in hemodynamics were observed. Two patients in the ketamine group, compared to zero in the morphine group, reported dreams as a side effect after bolus doses. There were significantly higher rates of nausea and vomiting in the morphine group (7 vs 0, $p < 0.01$).⁶

A prospective study with 38 patients was conducted to describe the analgesic efficacy and side effect profile of low dose ketamine for acute severe pain in the emergency department (ED). The study trialed a bolus of ketamine (15mg) as intravenous push (IVP) followed by slow infusion (20mg) over 60 min. Patients were offered morphine 4mg as rescue analgesia at the 20-, 40-, and 60-minute marks. Pain was assessed on a 10-point verbal numerical reading scale (NRS), along with vital signs and sedation scores frequently over 120 minutes. At the 60-minute mark, side effect rating scale for dissociative anesthesia (SERSDA) scale was used to assess side effects. Twenty-two patients had clinically significant reduction in pain at 10 minutes. Twenty-five patients had clinically significant reduction at the end of the infusion (60 minutes). Twelve patients did not require or refused adjunct morphine therapy, as pain was adequately controlled throughout the duration of the study. There was a significant proportion of patients that experienced side effects (33 patients, 86%) with a large portion grading them as weak or modest (20 patients, 53%). Thirteen patients (34%) reported side effects as “very bothersome”. The most common side effects were dizziness, fatigue, nausea and feeling of unreality. A large portion of patients (32 patients, 84%) reported they would trial ketamine again for pain management.⁷

A case series looked at 14 patients in an urban ED who received low dose ketamine (0.2-0.4mg/kg) infusions (10-15min) for analgesia. Thirteen patients had received analgesia prior to the ketamine infusion. No patient received rescue analgesia one hour post

infusion. There were no dangerous adverse effects noted. One patient reported tinnitus and uneasiness during the infusion while another reported dizziness.⁸

A recent study conducted in 2017 aimed to show reduction in side effects of LDK by giving it over 15 minutes compared to standard IVP of less than 5 minutes. A total of 48 patients were enrolled and the study showed similar rates of side effects except for overall feeling of unreality, which was significantly higher in IVP group (91.7% vs 54.2%, $p=0.008$). There were similar decreases in pain scores for each group ($p=0.14$) with no significant difference in use of rescue analgesia or change in vital signs.²

Another study published in 2018 mimicked the previously mentioned trial comparing LDK (0.3mg/kg) IVP (over one minute) and slow infusion (SI) over fifteen minutes, with a primary outcome of decreasing side effects. There were 59 participants that completed the study with a large reduction in psych perceptual side effects noted in SI group (43.4% vs 75.9%). There were also more participants that experienced hallucinations in the IVP group (8 vs 2). There was no difference in analgesic efficacy between the groups.⁹

Trials have shown that ketamine can be used as an adjunct to traditional analgesics with significant opioid sparing effects while maintaining, or even improving, analgesia.

A double blind, randomized, placebo trial was conducted with three groups in 2014. The three groups were morphine plus placebo (MP), morphine plus 0.15mg/kg ketamine (MK15), and morphine plus 0.3mg/kg ketamine (MK3). The purpose of this trial was to assess pain control with less opioid requirement. The study found that all groups had clinically meaningful decreases in overall pain scores. In both ketamine groups, there was a sustained decrease in pain score over two hours. While there were no vital sign abnormalities, there was a higher proportion of patients in the ketamine group that reported side effects, such as dizziness or lightheadedness.¹⁰

A prospective pre-hospital cohort study in 2009 compared morphine 0.2mg/kg (M) to morphine 0.1mg/kg plus ketamine 0.2mg/kg (MK) in respect to pain, nausea, sedation, and hemodynamics for acute bone fractures. There was a decrease in morphine quantity used when combined with ketamine ($13.5 \pm 3.2\text{mg}$ vs $7.0 \pm 1.5\text{mg}$). The mean ketamine dose was 27.9 ± 11.4 mg. Significant changes in pain on numeric rating scale were reported in favor of MK (3.1 vs 5.4) along with elevations in BP (167 vs 134). Side effects/adverse effects noted include nausea (4 patients vs 1) and vomiting in MK group (3 patients vs 0).¹¹

Based on the information from prior studies, ketamine has been proven to be a potent analgesic even when compared to standard of care morphine. The downside to ketamine

use seems to be due to the side effect profile that is bothersome to some patients. A previous study already showed improvement in side effects, mainly dizziness, when given over a longer period of time (15 minutes). We are hypothesizing that further increasing the administration duration will produce even less side effects while maintaining analgesic properties.

Literature reviews have been done that elaborate on the common side effects of ketamine when given for analgesia. One noted most common events to be nausea, altered mood, psychomimetic effects and headaches when given intravenously for complex regional pain.¹² Another article noted that there seemed to be psychomimetic effects along with hypertension when given for pain control via intravenous infusion, although appeared to improve after infusion was complete.¹³ Similar side effect profile in terms of psychomimetic effects has been seen in other studies and include dizziness, blurred vision, vertigo, nausea/vomiting, dysphasia, nystagmus, nightmares or vivid dreams, impaired motor function and memory deficit but like other studies, improves rapidly after infusion is complete. Cardiovascular effects secondary to the catecholamine release after administration have also been documented. The main effects appear to be tachycardia, hypertension and increase in cardiac output and recommend use of cardiac monitoring but do not seem to be long lasting effects.¹⁴

This study has been determined to be exempt from FDA IND requirements based on all criteria for exemption being met.

3. Study Design

The location of this study will be the Akron City Hospital Emergency Department. The trial will enroll approximately 48 evaluable subjects. An evaluable subject is defined as a subject who completes the entire infusion (30 minutes) and provides a 30 minute VAS and SERSDA score.

This will be an intent to treat prospective, double blind, double-dummy, randomized trial. The primary outcome will be a comparison of side effects of sub dissociative dose ketamine given by slow IV infusion over 15 minutes vs 30 minutes in treatment of moderate to severe acute pain in ED patients. The secondary outcome will be adequate pain control (VAS ≤ 5 cm(50mm)) and need for rescue analgesia between the two groups.

The control group will receive slow IV infusion of ketamine over 15 minutes. The experimental group will receive slow IV infusion of ketamine over 30 minutes.

If the patient meets all eligibility criteria, they will be consented by study staff members and then randomized to receive ketamine 0.25mg/kg in 100cc normal saline (NS), up to a

maximum of 30mg total dose, as an IV infusion over the specified time, as well as “placebo” 100cc NS over the other time slot.

[figure not shown]
If during the baseline assessment, immediately prior to the start of infusion, the subject reports an improved pain score (VAS < 5 cm(50mm)), the subject will be considered no longer eligible. The infusion will not be administered, and the subject will be removed from the study.

Since the subject was randomized, the group allocation (control or experimental group) for that subject will be reassigned to the randomization block to maintain a total of 48 enrolled (infused) subjects.

Pharmacy staff will provide the study medication in a blinded fashion to the nurse who will use infusion pumps to deliver both study medication and placebo simultaneously. Nursing staff will receive training on administration of the study medication prior to starting the study.

We will measure the side effect profile using the Side Effects Rating Scale for Dissociative Anesthetics (SERSDA) along with the Visual Analog Scale (VAS) (Appendix A).

Visual Analogue Scale scoring is done by asking the subject to mark the spot on the VAS Pain Assessment Tool (0-10cm) to indicate their perception of pain. Following this, the investigator scores the intensity of pain according to the 0-100mm corresponding scale (one instrument i.e., 5cm= 50mm). The VAS is a validated, subjective measure for acute and chronic pain. See below for exact tool that will be used.

Vital signs (heart rate, blood pressure, respiratory rate, and oxygen saturation) will also be obtained at 0, 5, 15, 30, 60, and 90 minutes from the start of the ketamine/NS placebo infusion.

Ketamine 30 min vs 15 min

Version: 7

Date: 06.06.2024

Page 7 of 15

Rescue Medication

At 30, 60 or 90 minutes post start of the ketamine infusion, if the study subject has a VAS score that is between 5-10cm (50-100mm), a **single** dose of both acetaminophen 1,000mg (oral) and ketorolac (15-30mg IV) will be given. If alternative medications are required, the study investigator will be consulted.

NOTE: EPIC recommends a ketorolac dose of 15mg IV if subject weight is less than 50kg or subject age is ≥ 65 years.

At 30 minutes post start of ketamine infusion, if the study subject has a VAS score that is between 8-10cm (80-100mm), fentanyl will be administered at 1mcg/kg up to 100mcg. (The dose will be calculated by EPIC to correspond to the nearest 0.05cc). If deemed safe and appropriate, the EPIC alert for doses greater than 100mcg may be overridden by the treating physician or study investigator to authorize doses greater than 100mcg (per institutional policy).

If the VAS score remains 8-10cm (80-100mm)) when assessed at 60 and 90 minutes post start of the ketamine infusion, the fentanyl dosing may be repeated.

NOTE: If the VAS score is assessed to be between 8-10cm (80-100mm) at any time point, and ketorolac and acetaminophen have **not** already been administered, ketorolac, acetaminophen and fentanyl may be given at the same time point.

NOTE: Ketorolac and acetaminophen may only be administered once during the study.

Study Termination

If rescue medication is administered, the patient will continue in the study and all data will be collected as outlined in the protocol as ITT (intent to treat).

If the subject experiences side effects which are unable to be managed in order to permit the continuation of the ketamine infusion, it will be stopped. All data will continue to be collected according to the protocol and the subject will continue to be observed for the remainder of the 90-minute study period, unless the subject withdraws their consent to participate.

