3.1 Subject Population

Inclusion and Exclusion Criteria

Ketamine 30 min vs 15 min

Version: 7

Date: 06.06.2024

Page 8 of 15

Inclusion criteria:

- Patients 18 years of age or older
- Primary complaint of acute moderate to severe pain on VAS/numeric pain scale (a score of ≥ 5 cm which corresponds to 50mm).
- Pain described as abdominal, flank, back, musculoskeletal, or traumatic chest pain
- Must be alert and oriented times three
- Able to provide informed consent.

Exclusion criteria:

- Pregnant
- Breastfeeding
- Altered mental status
- Known or reported allergy, hypersensitivity, or intolerance to ketamine
- Unstable vital signs (systolic blood pressure < 80 or > 180 mmHg, heart rate < 50 or > 150 beats per minute, and respiratory rate < 10 or > 30 breaths per minute)
- History of unstable heart disease, such as arrhythmias, congestive heart failure, or coronary heart disease.
- History of untreated or uncontrolled thyroid disease
- Acute head or eye injury
- Active or current abuse of alcohol or illicit drugs
- Known intracranial hypertension
- Hepatic or renal insufficiency
- Current active manic phase of bipolar disorder
- Active delusions, hallucinations, or schizophrenia
- Patients who have recent fentanyl use within 60 minutes or other analgesic use (opiates) within 4 hours of study enrollment (signing of consent)
- Patients who have enrolled in the study during a previous ED encounter
- Chronic use of opiates (i.e.: fentanyl patch, SR opiates)

It will be at the discretion of the treating ED physician who is taking care of the patient to determine whether the patient is appropriate for the study. If it is determined the patient requires a more urgent form of pain control intervention, the patient will be excluded.

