3.3 Outcomes/Objectives

The primary objective of this study is to attempt to prove that increasing the length of ketamine administration decreases overall incidence and severity of side effects. The side effects to be monitored include fatigue, dizziness, headache, feeling of unreality, hearing, vision, or mood changes, generalized discomfort, and hallucinations. Our goal is to have at least a 20% decrease in overall scores, which equals to a “1” point decrease on the SERSDA scale. SERSDA measures severity of nine adverse effects based on a 5-point scale from “0” (no adverse effect) to “4” (very bothersome effect).

The primary outcome measure of this study is the reduction of the overall side effects as measured by the Side Effect Rating Scale for Dissociative Anesthetics (SERSDA) at 30 minutes.

The secondary objective is to ensure that adequate pain control (VAS ≤ 5 cm) is maintained when ketamine administration is prolonged. To do this we will be measuring pain scores on the 100mm VAS at each protocol specified interval (0, 5, 15, 30, 60 and 90 minutes from the infusion start time, which is defined as time zero). Studies have shown that for clinical significance in pain reduction, there needs to be at least a 13mm difference on the 100mm VAS pain scale.¹⁵

Ketamine 30 min vs 15 min

Version: 7

Date: 06.06.2024

Page 10 of 15

The secondary outcome measure is the severity of self-reported pain on the standard 100mm VAS pain scale (0-100) at 30 minutes.

The need to administer rescue analgesic medication will also be assessed, starting at 30 minutes and again at 60 and 90 minutes post start of the infusion (Time 0).

We will also be monitoring the need for the administration of other interventions to treat ketamine side effects (nausea etc.), as well as vital signs.

The Richmond Agitation Sedation Scale (RASS) (Appendix A) will be used to collect additional data.

Study Schedule

	Time 0 min	Time 5 min	Time 15 min	Time 30 min	Time 60 min	Time 90 min
VITAL SIGNS	X	X	X	X	X	X
SERDSA		X	X	X	X	X
VAS	X	X	X	X	X	X
RASS		X		X		X

4. Data Analysis/Plan

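### At exactly 5 cm (50 mm) the VAS rules conflict: the same score qualifies for entry, counts as adequate pain control and, read inclusively, triggers rescue

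*Combined protocol and SAP*

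**What the plan says.** Four rules use the same VAS cut-off.

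- **Entry** (section 3.1): "a score of ≥ 5 cm which corresponds to 50mm".
- **Pre-infusion check** (section 3): if "the subject reports an improved pain score (VAS < 5 cm(50mm)), the subject will be considered no longer eligible". A score of exactly 5 cm does not remove the subject.
- **Success**: section 1 sets the aim as a "Visual Analogue Score (VAS) of ≤ 5 cm (50mm) at 30 minutes after start of ketamine infusion", and its hypothesis uses the same cut-off. Section 3 lists "adequate pain control (VAS ≤ 5 cm(50mm)) and need for rescue analgesia" as the secondary outcome. Section 3.3 says "The secondary objective is to ensure that adequate pain control (VAS ≤ 5 cm) is maintained when ketamine administration is prolonged".
- **Rescue** (section 3, Rescue Medication): at 30, 60 or 90 minutes, medication is given "if the study subject has a VAS score that is between 5-10cm (50-100mm").

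Section 3 states that the centimetre and millimetre scales are one instrument, with 5 cm equal to 50 mm. Section 3.3 starts the assessment of rescue at 30 minutes, the time point of the pain-control aim. It also names the 30-minute VAS score itself, with no cut-off, as the secondary outcome measure, and it takes 13 mm as the smallest clinically significant change. No passage says how a score of exactly 50 mm is to be handled.

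**The concern.** Two overlaps follow.

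The first is between entry and success. A score high enough to qualify as the pain under treatment is also low enough to count as controlled. A subject can therefore be a success without changing at all. The same subject would count among those without a clinically significant reduction under the stopping rule in section 5, which uses the 13 mm standard.

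The second is between success and rescue. Section 3 reports adequate control and need for rescue side by side as the secondary outcome. If the rescue range includes its lower limit, one score at one assessment puts a subject in both categories.

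At stake are the meaning of the adequate-control rate, which is written into the hypothesis, and a choice between two definitions that would otherwise be made after the data are seen.

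**Working it through.** **Plan's own figure.** The only figure in the plan that can be recomputed is the sample size in section 4: difference 1 unit, SD 1.2, two-sided alpha 5%, power 80%. The normal approximation gives n = 2 × (1.96 + 0.84)² × 1.2² / 1² = 22.6, so 23 per arm. The t-test version gives 23.6, so 24 per arm, with 80.7% power. The planned 24 is reproduced. It rests on SERSDA, so nothing below changes it.

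**Rules on the 0-100 mm scale.**

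| Rule | Scores | Includes 50? |
|---|---|---|
| Entry (3.1) | 50 to 100 | yes |
| Stays in at pre-infusion check (3) | 50 to 100 | yes |
| Success (1, 3, 3.3) | 0 to 50 | yes |
| Rescue, inclusive reading (3) | 50 to 100 | yes |

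The intersection of all four is {50}. At every other score the success and rescue rules agree.

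**Sensitivity to the reading of the rescue range.** If the lower limit is excluded, rescue covers scores above 50. Success and rescue then have no score in common, but entry and success still share {50}. The first overlap does not depend on the reading; the second does.

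**Who is reclassified.** Replacing ≤50 by <50 changes the result only for a 30-minute score of exactly 50. Someone who enters at 50 and scores 30 or 70 at 30 minutes is classified the same either way.

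**Size.** One subject in an arm of 24 is 1/24 = 4.2 percentage points. The share s of subjects at exactly 50 mm at 30 minutes is not in the documents, so it is an assumption. The expected number is 48 × s, and the chance of at least one is 1 − (1 − s)^48.

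| Assumed s | Expected of 48 | Chance of at least one |
|---|---|---|
| 1% | 0.5 | 38% |
| 2% | 1.0 | 62% |
| 5% | 2.4 | 91% |
| 10% | 4.8 | 99% |

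**Effect on the comparison.** Let pA and pB be the shares below 50 mm in the two arms, and let the same share x sit at exactly 50 mm in each. Under the ≤50 rule the difference is (pA + x) − (pB + x) = pA − pB, the same as under the <50 rule.

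**Check of the fix.** With success at 0 to 49 and entry and inclusive rescue at 50 to 100, no score is in both. At 30 minutes success and rescue are then exact complements.

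**The case against.** The case for leaving this alone is that it is one boundary symbol. Section 3.3 makes the continuous 30-minute VAS score the secondary outcome measure, and section 4 assigns continuous outcomes to a mixed model; neither depends on the cut-off. Section 4 names Fisher's exact or chi-square tests for adverse event rates and no test for a pain-control rate. The second overlap needs the rescue range read as inclusive, which no symbol states. Need for rescue is also assessed at 60 and 90 minutes, so the documents do not require it to mirror the 30-minute endpoint throughout. All of this stands, and it limits the weight of the point. It does not supply a rule for 50 mm, and the entry overlap does not depend on the inclusive reading.

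It is also fair to say that moving the cut-off to below 50 mm does not ensure benefit: a fall from 50 to 49 mm would be a success, far short of 13 mm. The change removes the contradiction between rules and nothing more.

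A reader might infer that the overlap inflates success in both arms, pulls them together and so favours the conclusion that analgesia is maintained. The documents do not support that. Equal shares at 50 mm leave the difference unchanged, and nothing shows unequal shares. Nor does it follow that every subject entering at 50 mm is misclassified; only the 30-minute score matters.

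**Conclusion.** The conflict is real and confined to one score. A subject who enters at 50 mm and does not change counts as adequately controlled. On the inclusive reading, any subject at 50 mm at 30 minutes is reported as both controlled and needing rescue.

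The effect is 4.2 percentage points on an arm's adequate-control rate per such subject. About 1-5 of 48 subjects are affected if 2-10% score exactly 50 mm; that range is an assumption with no source in the documents. The point concerns the reported rate and the clarity of its definition. It is not evidence of a biased treatment comparison, and it leaves the continuous VAS outcome, the primary outcome and the sample size untouched. It should be corrected because the definition appears in the aims, the hypothesis, the design and the objectives, and because the correction costs almost nothing.

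**What to change.** Reconcile the entry, pre-infusion, success and rescue passages at 5 cm before unblinding, and state explicitly whether the rescue range includes its lower limit. Define the dichotomous analysis endpoint so that it excludes any score that meets the entry criterion or the 30-minute rescue trigger. With those rules as now written, that is VAS below 50 mm at 30 minutes, to be entered in section 1 (aims and hypothesis), section 3 and section 3.3. If the investigators revise the clinical thresholds instead, the endpoint should follow them. No position is taken here on what those thresholds should be.

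The cost is one symbol in the endpoint definition. VAS is already scored in millimetres, so no new data are needed. The reported adequate-control rate may be slightly lower.
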